The above mentioned tests and assessment are to be performed within 28 days of Rituximab & Zevalin administration.

d. Rituxaimab Infusion (250 mg/m²) & ¹¹¹In Zevalin (Ibritumomab Tiuxetan Indium) infusion. (Please refer to section 7.B for detailed treatment administration)

5.C.2 Days 2, 3, 4 and 5

a. Gamma Scan: A scan is to be performed at 48-72 hours after ¹¹¹In Zevalin (Ibritumomab Tiuxetan Indium) infusion. Another optional scan may be performed at 90-120 hours after ¹¹¹In Zevalin (Ibritumomab Tiuxetan Indium) infusion.

CAUTION WILL BE TAKEN IN THE HANDLING OF ALL RADIOACTIVE SAMPLES ACCORDING TO STANDARD PROCEDURES AND PRACTICES AT THE CLINICAL SITE

The purpose of ¹¹¹In Zevalin (Ibritumomab Tiuxetan Indium) imaging is twofold:

- To evaluate biodistribution of whole body gamma camera images
- To assess whether biodistribution is acceptable to proceed with ⁹⁰Y Zevalin (Ibritumomab Tiuxetan Ytrium-90) radioimmunotherapy.

The biodistribution of ¹¹¹In Zevalin (Ibritumomab Tiuxetan Indium) should be assessed by a visual evaluation of whole body planar view anterior and posterior gamma images. A set of images at 48-72 hours after injection is required. To resolve ambiguities, optional images at other time points may be necessary. Images should be acquired using a large field of view gamma camera quipped with a medium energy collimator. Whole body anterior/posterior planar images should be acquired using a large field-of-view gamma camera and medium energy collimators. Suggested gamma camera settings: 256 x 1024 matrix; dual energy photopeaks set at 172 and 247 keV; 15% symmetric window; scan speed of 10 cm/min for the 48-72 hour scan, and 7-10 cm/min for subsequent scans.

> Expected biodistribution:

- Activity in the blood pool areas (heart, abdomen, neck, and extremities) may be faintly visible.
- Moderately high to high uptake in normal liver and spleen.
- Moderately low or very low uptake in normal kidneys, urinary bladder, and normal (uninvolved) bowel.
- Non-fixed areas within the bowel lumen that change position with time; delayed imaging as described above may be necessary to confirm gastrointestinal clearance.

Tumor uptake may be visualized in soft tissue as areas of increased intensity, and tumor-bearing areas in normal organs may be seen as areas of increased or decreased intensity. Tumor visualization on the ¹¹¹In Zevalin (Ibritumomab Tiuxetan Indium) scan is not required for ⁹⁰Y Zevalin (Ibritumomab Tiuxetan Ytrium-90) therapy.

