➤ Altered biodistribution

- Intense localization of radiotracer in the liver and spleen and bone marrow indicative of reticuloendothelial system uptake
- Increased uptake in normal organs (not involved by tumor) such as:
 - o Diffuse uptake in normal lung more intense than the liver.
 - o Kidneys with greater intensity than the liver on the posterior view.
 - o Fixed areas (unchanged with time) of uptake in the normal bowel greater than uptake in the liver.
 - o In less than 0.5% of patients receiving ¹¹¹In Zevalin (Ibritumomab Tiuxetan Indium), prominent bone marrow uptake was observed, characterized by clear visualization of the long bones and ribs.

If a visual inspection of the gamma images reveals an altered biodistribution, the patient should not proceed to the ⁹⁰Y Zevalin (Ibritumomab Tiuxetan Ytrium-90) dose. The safety and efficacy of the administration of ⁹⁰Y Zevalin (Ibritumomab Tiuxetan Ytrium-90)in patients with prominent marrow uptake is not known. Possible causes of prominent bone marrow uptake, such as bone marrow involvement by lymphoma, increased marrow activity due to recent hematopoietic growth factor administration, and increased reticuloendothelial uptake in patients with HAMA and HACA, should be considered. Re-assessment of biodistribution after correction of underlying factors should be performed. ⁹⁰Y Zevalin (Ibritumomab Tiuxetan Ytrium-90) should not be administered to patients with persistently prominent marrow uptake on the repeat biodistribution scans.

5.C.3 Day 7, 8 or 9

a. Rituximab Infusion & ⁹⁰Y Zevalin (Ibritumomab Tiuxetan Ytrium-90) Infusion (Please refer to section 7.B for detailed treatment administration)

5.C.4 Day 35 (+/- 7 days)

a. Laboratory tests including:

Complete blood count (CBC) with differential and platelet count. To be done every week until any count abnormalities have passed nadir.

5.D Restaging

5.D.1 3 Months Post-90Y Zevalin (Ibritumomab Tiuxetan Ytrium-90) Infusion

The following tests/evaluations will be obtained 3 months (+/- 7 days) post ⁹⁰Y Zevalin Infusion:

- a. History & Physical examination, including vital signs (BP, temperature & pulse), height, weight, Body Surface Area (BSA) & performance status (Appendix B).
- b. Laboratory tests including:
 - Complete blood count (CBC) with differential and platelet count
 - Serum chemistries BUN, creatinine
 - LDH
- c. Disease Assessment:
 - Total of all measurable indicator lesions.
 - CT or PET scan of the chest, abdomen and pelvis

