The radiolabeling kits should be stored in a secure refrigerator at 2 - 8°C. Zevalin solutions are stable at 2 - 8°C for up to 8 hours for ⁹⁰Y Zevalin and up to 12 hours for ¹¹¹In Zevalin following their preparation. Due to the relatively short half life of the ⁹⁰Y isotope, if not used soon after calibration time, the actual dose will have decayed and will require recalculation. For proper Rituxan storage instructions see the package insert in the appropriate Appendix.

6.C.5 111In Zevalin and 90Y Zevalin Treatment Protocol

The ¹¹¹In and ⁹⁰Y isotope order form must be completed and faxed to the designated isotope vendor preceding the initial Rituxan infusion. Patients will receive an initial infusion of 250 mg/m² Rituxan. (111 In Zevalin, 90-Y-Zevalin, and Rituximab will not be provided by Biogen Idec

Incorporated). Immediately following, patients will receive a fixed dose of 5.0 mCi of ¹¹¹In Zevalin. If the biodistribution is altered such that the safety risk would be unacceptable, the patient will be taken off study and not proceed with ⁹⁰Y Zevalin radioimmunotherapy. On Day 7, 8 or 9, patients must receive a second infusion of 250 mg/m² of Rituxan and either 0.4 mCi/kg or 0.3 mCi/kg of Zevalin based on most recent platelet counts. The exact dose of Zevalin will be based on the patient's weight during the most recent evaluation according to Table 4. **The maximum dose is not to exceed 32 mCi of ⁹⁰Y.**

Table 4. Dosing of Zevalin

Platelet Counts ≥ 150,000/mm ³	Platelet Counts 100,000/mm ³ to 149,000/mm ³
0.4 mCi ⁹⁰ Y/kg	0.3 mCi ⁹⁰ Y/kg
Dose will be calculated using actual body weight	Dose will be calculated using actual body weight
Not to exceed 32 mCi (Maximum Dose)	Not to exceed 32 mCi (Maximum Dose)

6.C.6 Zevalin Adverse Events

For an extensive review of adverse events refer to the Investigational Brochure. Safety data, except where indicated, are based upon 349 patients treated in 5 clinical studies with ZEVALIN. In all cases, the ZEVALIN regimen included two doses of RITUXAN. See the RITUXAN package insert for specific adverse event (AE) information for that product.

Table 5 lists most common nonhematologic adverse events in \geq 5% of patients. The table does not include hematologic AEs of neutropenia, thrombocytopenia, and anemia (See Table 6, Hematologic Toxicity).

 $Table \ 5$ Incidence of Nonhematologic† Adverse Events in ≥ 5 % of Patients in Clinical Trials with ZEVALIN Regimen During the Treatment Period*(N = 349)

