7 TREATMENT PLAN

All patients who qualify for this study will receive chemotherapy with ESHAP followed by treatment with Zevalin

7.A ESHAP REGIMEN DOSING

ESHAP chemotherapy: Patients will receive 2 cycles of cytoreductive chemotherapy according to the schedule described below. (Table 7)

TABLE 7 ESHAP CHEMOTHERAPY PLUS ZEVALIN

DRUG	DOSE	ROUTE	DAYS	INTERVAL
Etoposide	$40 \text{ mg/m}^{2/} \text{day}$	IV infusion over 1 hour	1,2,3,4	q 28 days for 2 cycles
Methylprednisolone	250 mg/day	IV push	1,2,3,4	q 28 days for 2 cycles
		_		
Cytarabine	2000 mg/m^2	IV infusion over 2 hours	4	q 28 days for 2 cycles
Cisplatin	25 mg/m ² /day	IV infusion at 1mg/min	1,2,3,4	q 28 days for 2 cycles

- The cycle length will be 28 days if bone marrow recovery allows. If recovery requires an additional week, then the second cycle will be postponed for a week.
- Either pegfilgastrim or filgastrim may be given at the investigator's discretion.

7.B RITUXIMAB, 111 IN ZEVALIN, AND 90 Y ZEVALIN ADMINISTRATION

The rituximab + ibritumomab tiuxetan regimen is given 4-6 weeks after completion of the second cycle of ESHAP. Treatment can be completed within 7 - 9 days in an outpatient setting

TABLE 8
Rituximab, 111In Zevalin, AND 90Y Zevalin Administration

AGENT	DOSE	ROUTE	DAYS	NOTES
Rituximab	250 mg/m ²	Slow IV	1, then 7, 8 or 9	Give prior to 111 In Zevalin
¹¹¹ In Zevalin	5 mCi	Slow IV push over 10 minutes	1	Give within 4 hours after rituximab
⁹⁰ Y Zevalin	Depends on platelet count (see Section 7.B.3)	Slow IV push over 10 minutes	7, 8, or 9	Give within 4 hours after rituximab

7.B.1 Rituxan & 111 In Zevalin Administration

1.6 mg of ¹¹¹In Zevalin (5.0 mCi of ¹¹¹In) will be used for radioimaging. The imaging dose of ¹¹¹In Zevalin will be administered by a 10-minute slow IV push injection immediately following the infusion of Rituxan. ¹¹¹In Zevalin may be directly injected by stopping the flow from the IV bag and injecting the radiolabeled antibody directly into the line. A 0.22 micron filter must be on line between the patient and the infusion port. Flush the line with at least 10 mL of normal saline after ¹¹¹In Zevalin has been injected. (See Appendix H).

a. Oral premedication (2 tablets [325 mg] of acetaminophen and 50 - 100 mg oral diphenhydramine hydrochloride) may be administered 30 - 60 minutes prior to starting each infusion of rituximab.

7.B.2 Radioimaging Schedule

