Please note: Patients with platelet counts from $100,000/\text{mm}^3$ to $149,000/\text{mm}^3$ will receive 0.3 mCi/kg and patients with platelet counts $\geq 150,000/\text{mm}^3$ will receive 0.4 mCi/kg, not to exceed 32 mCi $\frac{90\text{Y Zevalin}}{\text{Zevalin}}$. 90Y Zevalin will be administered intravenously as a slow IV push over 10 minutes. 90Y Zevalin may be directly infused by stopping the flow from the IV bag and injecting the radiolabeled antibody directly into the infusion port. A 0.22 micron filter must be on line between the syringe and the infusion port. Flush the line with at least 10 mLs of normal saline after 90Y Zevalin has been infused. (See Appendix H for radioincorporation methods)

There is no provision for additional treatment courses for patients entered into this protocol.

- a. Oral premedication (2 tablets [325 mg] of acetaminophen and 50 100 mg oral diphenhydramine hydrochloride) may be administered 30 60 minutes prior to starting each infusion of rituximab.
- b. Y-90 ibritumomab tiuxetan should be dosed at 0.4 mCi/kg (14.8 MBq/kg) actual body weight for patients with platelets counts ≥ 150,000/mm³ and at 0.3 mCi/kg (11.1 MBq/kg) actual body weight for patients with platelet counts of 100,000 149,000/mm³. The prescribed, measured and administered dose of Y-90 ibritumomab tiuxetan must not exceed the absolute maximum allowable dose of 32.0 mCi (1,184 MBq), regardless of the patient's body weight. Do not give Y-90 ibritumomab tiuxetan to patients with a platelet count < 100,000/mm³.
- c. Radiation Safety Precautions are minimal: No isolation required. Observe the following guidelines for 7 days after Y-90 Zevalin Patients should wash their hands thoroughly after urinationThe use of a condom is recommended during sexual intercourse to avoid transfer of body fluids. Avoid deep kissing. Throughout therapy and for up to 12 months following treatment, effective contraception is recommended.

d. Granulocyte colony stimulating factors may be given at the discretion of the treating physician to prevent or mitigate unacceptable granulocytopenia associated with fever, or granulocytopenia less than 500 granulocytes/µl. The use of G-CSF must be documented on the treatment summary form. Any toxicities associated with G-CSF must also be documented on the adverse event form.

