Patients experiencing Grade 3 cisplatin neuropathy (e.g., loss of motor function) will have the dose reduced by 50% for all further cycles of ESHAP. Patients experiencing Grade 4 neuropathy will have the cisplatin omitted from all further cycles of ESHAP. Patients experiencing Grade 3 cytarabine neuropathy with ESHAP cycle 1 will have the dose reduced by 50% for cycle 2. Patients experiencing Grade 4 or worse cytarabine neuropathy will have the cytarabine omitted from all further cycles.

8.B Rituximab Antibody Toxicities & Dose Modifications

8.B.1 Fevers:

Patients may experience transient fever and rigors with infusion of chimeric anti-CD20 antibody. If Grade 3 fever (or Grade 2 fever with rigors) or Grade 2 rigors are noted, the antibody infusion should be temporarily discontinued, the patient should be observed, and the severity of the side effects should be evaluated. The patient should be treated according to the best available local practices and procedures. Following observation, when fever resolves to Grade 2 or less and rigors to Grade 1 or less, the infusion should be continued, initially, at 1/2 the previous rate. Following the antibody infusion, the IV line should be kept open for medications, as needed.

8.B.2 Hypersensitivity:

Hypotension, bronchospasm or angioedema have occurred as part of an infusion-related symptom complex. If a Grade 3 or greater hypersensitivity/allergic reaction occurs, rituximab infusion should be interrupted and may be resumed at a 50% reduction in rate when symptoms have completely resolved. Treatment with diphenhydramine and acetaminophen is recommended; additional treatment with bronchodilators or IV saline may be used at the physician's discretion. Precautionary hospitalization for patients experiencing severe infusion symptoms which do not resolve after discontinuation of the cycle is recommended.

8.B.3 Observation post Infusion

If there are no complications, the IV line may be discontinued after 1 hour of observation. If complications occur during the rituximab infusion, the patient should be observed for 2 hours after the completion of infusion. If a patient experiences a Grade 3 toxicity that persists until the next scheduled infusion, the patient must discontinue treatment until toxicities have resolved to Grade 2 or less. If treatment is delayed for more than 3 weeks, call the Study Coordinator.

8.B.4 Tumor Lysis Syndrome:

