APPENDIX A

STUDY CALENDAR

4/1/2010

STUDY CALENDAR Page 1

					Ibritumomab Tiuxetan (Zevalin)			
Required Studies	Baseline	ESH	AP Treatm	ent		Regin	nen [∞]	
Visits (weeks or days)	Within28 days prior to C1, D1	Cycle 1 Day 1	Cycle 2 Day1	Cycle 2 Day 29	Day 1	Day 2,3,4,5	Day 7, 8, or 9	Day 35
PHYSICAL								
History / Physical / vital signs ^α	X		X	X	ΧП			
Height / Weight / BSA / PS	X		X	X	ΧП			
Disease Assessment	X			X				
Toxicity Assessment	X		X	X	ΧП			
LABORATORY								
CBC / differential / platelets	X		X	X	ΧП			\mathbf{X}^{Σ}
Serum Creatinine / BUN	X		X	X	ΧП			
AST/ ALT/ Alk. Phos/ T. Bilirubin^	X							
LDH	X							
BHCG [†]	X							
Beta 2- microglobulin	X							
Hepatitis B screen*	X							
Pathology Review [£]	X							
Bone marrow cytogenetics [¥]	X			X				
Bone marrow aspiration and Bx	X			X				
SCANS								
CT or PET Chest	X			X				
CT or PET Abdomen	X			X				
CT or PET Pelvis	X			X				
Gamma Scan						X≠		
TREATMENT								
ESHAP		X	X					
Rituximab 250 mg/m2					X		X	
Ibritumomab Tiuxetan Indium (¹¹¹ In Zevalin)					X			
Ibritumomab Tiuxetan Ytrium-90 (90Y Zevalin)							X	

- α Vital Signs consist of BP, temperature and pulse
- t Baseline for women of childbearing potential
- ¥ A scan is performed at 48-72 hours after 111In Zevalin. Another optional scan may be performed at 90-120 hours after 111In Zevalin.
- ∞ ¹¹¹In Zevalin is administered 4-6 weeks after completion of ESHAP.
- ٨ Required at Baseline and Encouraged to repeat as clinically indicated by Good Medical Practice.
- Encouraged by Good Medical Practice, but not required.
- ¥ Bone Marrow cytogenetics can be done at either Baseline or C2,D29, but must be done at least once.
- £ Pathology Review consists of a basic review of a pathology report. If possible submit: Representative H&E stained slides from the diagnostic biopsy, one representative paraffin block and one copy of the pathology report.
- Σ Starting Day 35 (+/- 7 days) a CBC w/ Diff and Platelet count should be done every week until nadir.
- Within 28 days prior to Rituximab & Zevalin administration..

STUDY CALENDAR Page 2

Required Studies	Restaging	Short-Term Follow-Up				Long-Term Follow-Up	Off-Study [#]
Visits (weeks or days)	3 mos post ⁹⁰ Y Zevalin	6 mos post Zevalin	12 mos post Zevalin	18 mos post Zevalin	24 mos post Zevalin	Follow-Up: Annually for 3 years [£]	Disease Progression or Removed from Study (within 4 weeks)
PHYSICAL							
History / physical / vital signs ^α	X	X	X	X	X	X	X

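### No section clearly requires a current platelet count before the single 90Y dose, and an 8.B.3 toxicity hold can age the count by up to 21 more days before that section's call is due

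*Combined protocol and SAP*

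**What the plan says.** Section 6.C.5 fixes the timing: "On Day 7, 8 or 9, patients must receive a second infusion" of rituximab, and with it "either 0.4 mCi/kg or 0.3 mCi/kg of Zevalin based on most recent platelet counts". It gives no maximum age for that count. Table 8 in section 7.B ties 90Y to the rituximab infusion: "Give within 4 hours after rituximab". Section 7.B.3b adds a floor, "Do not give Y-90 ibritumomab tiuxetan to patients with a platelet count" below 100,000/mm3, without saying when the count must be drawn.

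The blood count before treatment is listed in section 5.C.1, under Zevalin Day 1: "The above mentioned tests and assessment are to be performed within 28 days of Rituximab & Zevalin administration". The Appendix A footnote reads "Within 28 days prior to Rituximab & Zevalin administration". Appendix A marks a count at Zevalin Day 1 and at Day 35, and none in the Day 7, 8 or 9 column.

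Section 8.B.3 covers a Grade 3 toxicity that persists to the next scheduled infusion. Treatment stops "until toxicities have resolved to Grade 2 or less. If treatment is delayed for more than 3 weeks, call the Study Coordinator". It asks for no blood count on resuming. Sections 6.C.5 and 8.B.3 do not refer to each other.

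**The concern.** The dose of 90Y is given once and cannot be withdrawn. Section 1.D.2, in its dosimetry summary, says that hematologic toxicity did not track any dosimetric or pharmacokinetic measure examined, and that patients were treated safely by dosing on weight and platelet count. The platelet count is therefore the main dosing safeguard, and a schedule that lets it grow old weakens that safeguard.

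Two errors are possible. Platelets that have fallen below 150,000/mm3 unseen lead to 0.4 mCi/kg where Table 4 intends 0.3. Platelets that have fallen below 100,000/mm3 unseen lead to a dose that section 7.B.3b prohibits. Section 6.B.2 records transient platelet falls after rituximab, which is given on Zevalin Day 1. In Table 6, patients with mild baseline thrombocytopenia had a median platelet nadir of 24,000/mm3 and 14% Grade 4 toxicity even at 0.3 mCi/kg. The figures were 41,000/mm3 and 10% for patients with normal platelets at 0.4 mCi/kg.

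**Working it through.** The plan states no maximum count age, so there is no figure of its own to reproduce. The check is day arithmetic.

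**Does a hold move 90Y?** After the Day 1 rituximab, the only remaining scheduled rituximab is on Day 7, 8 or 9 (section 6.C.5, Table 8), and 90Y follows it within 4 hours. A section 8.B.3 hold therefore moves both. A 21-day delay, the longest that does not trigger that section's call, puts 90Y on Day 7 to 9 + 21 = Day 28 to 30.

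**How old can the count be?** Let *a* be the days from the count to Zevalin Day 1, and *D* the day of 90Y. Age at 90Y = *a* + (*D* − 1).

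- If the 28-day window runs to Zevalin Day 1, *a* is at most 28.
- A count is also scheduled at ESHAP Cycle 2 Day 29 (section 5.B.3). Zevalin starts 4 to 6 weeks after ESHAP is completed (section 5.C). If completion means the last drug day, Cycle 2 Day 4, then Zevalin Day 1 is Cycle 2 Day 4 + 28 = 32 to 4 + 42 = 46. The Day 29 count is then 3 to 17 days old, so *a* is at most 17.
- If the window runs to 90Y itself, the age is at most 28 by definition.

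| Reading | Largest *a* | 90Y on Day 7–9 | 90Y on Day 28–30 |
|---|---|---|---|
| Window to Zevalin Day 1 | 28 | 34–36 days | 55–57 days |
| Same, ESHAP completed on Cycle 2 Day 4 | 17 | 23–25 days | 44–46 days |
| Window to 90Y | – | at most 28 days | at most 28 days |

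Even on the last reading, a count drawn on Zevalin Day 1, before any hold, is 27, 28 or 29 days old on Day 28, 29 or 30. It still qualifies through Day 29.

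**Does another scheduled count intervene?** Section 5.C.4 places the next one at Day 35 ± 7, so Day 28 at the earliest and Day 42 at the latest, then "To be done every week until any count abnormalities have passed nadir". It follows the nadir and need not precede a delayed dose.

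**Does the restart rule protect the floor?** No. The footnote to Table 6 places Grade 3 or 4 platelets below 50,000/mm3. A patient at Grade 2 or less can therefore still be under 100,000/mm3.

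**What would a missed fall below 150,000/mm3 cost?** Excess = min(0.4*w*, 32) / min(0.3*w*, 32) − 1, for weight *w* in kg and the 32 mCi cap. The cap binds from 32/0.4 = 80 kg at the higher dose and from 32/0.3 = 106.7 kg at the lower. The weights are examples.

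| Weight | Given v. intended (mCi) | Excess |
|---|---|---|
| 70 kg | 28 v. 21 | 33% |
| 80 kg | 32 v. 24 | 33% |
| 90 kg | 32 v. 27 | 19% |
| 100 kg | 32 v. 30 | 7% |
| 107 kg | 32 v. 32 | 0% |

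**How does the protocol treat similar delays?** Section 8.A.1 has counts repeated when ESHAP is delayed for low counts, and section 8.B.4 requires contact before resuming after tumor lysis. Section 8.B.3 has neither safeguard.

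**The case against.** A reader might infer that sections 6.C.5 and 8.B.3 contradict each other. The documents do not support that. Section 8.B.3 is a toxicity hold in the dose-modification section and reads as a specific exception to the standard schedule. Section 7.B says only that treatment can be completed in 7 to 9 days, and section 5.C.2 foresees repeat biodistribution assessment before 90Y. What is missing is a cross-reference.

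A reader might also infer that the hold creates the problem, or that no count is ever required. Neither follows. An old count is possible with no hold at all, and the 28-day wording can be read to cover 90Y, which would force a new count in some held patients. The text is ambiguous, not silent.

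The second phone registration in section 13.B confirms dose before Zevalin starts. Because the 111In dose is fixed, that call may be read as preceding 90Y in every patient. This stands in part: the section does not ask for a new count, and a delay does not trigger the call.

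The harm pathway is also limited. Section 6.B.2 describes hematologic toxicity after rituximab as usually mild and reversible. Section 6.A.1 puts recovery of counts after cisplatin at about three weeks, so an older count may understate platelets. Table 6 does not show 0.4 mCi/kg in mild thrombocytopenia and so does not measure the harm of misdosing. Infusion reactions generally settle with slowing or interruption, and a hematologic hold would normally produce a fresh count anyway. These points lower the expected frequency. They do not supply the missing requirement.

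**Conclusion.** The gap is real and belongs to the count schedule. The age of the count at an on-time 90Y can reach 34 to 36 days, 23 to 25 days or 28 days, depending on the reading. Where the window runs to Zevalin Day 1, a hold adds up to 21 days before section 8.B.3 asks for a call. The 55 to 57 day figure should not be read as typical: it needs the 28-day window to run to Zevalin Day 1, ESHAP completion to mean the end of the cycle, a draw at the edge of the window and a full 3-week hold. On the earlier completion reading the figure is 44 to 46 days.

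The possible dosing error is up to 33% excess activity, falling to none from about 107 kg, or a dose given below the platelet floor. Its frequency is unknown. The documents give no rate of Grade 3 toxicity persisting to Day 7 to 9, and it is probably low. The sample size of 52 and the evaluable set are unaffected. The change is worth making because the dose is irreversible and the safeguard is one routine test.

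**What to change.** - **Appendix A (Day 7, 8 or 9 column) and section 7.B.3b:** require a CBC with platelets shortly before 90Y in every patient, for example within 3 days. State that this count sets the dose by Table 4 and that 90Y is not given below 100,000/mm3. The 3-day limit is a proposal; the documents give none.
- **Section 8.B.3:** require that this count be taken after the hold, and that the Study Coordinator be called before resuming if 90Y will fall after Day 9.
- **Section 6.C.5:** after the Day 7, 8 or 9 timing, add (later only as in 8.B.3).

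The cost is one routine blood count per patient and one call per held patient. No infusion, scan or patient is added. Some patients will be moved to 0.3 mCi/kg or lose 90Y because of the new count, which is what Table 4 and section 7.B.3b already intend.
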